11.4.2. Pharmacokinetic/Pharmacodynamic/Biomarker Analyses (Edoxaban Subjects Only)

Plasma concentration and biomarker data will be summarized by age, dose and time point using descriptive statistics. The plasma concentration data will be pooled with data from other studies for a population PK analysis using nonlinear mixed effects modeling.

Exposure-response relationships will be evaluated for the safety and efficacy endpoints through a model based approach, if data allow, and will be reported separately.

Pharmacokinetic and pharmacodynamics data will be analyzed separately and reported separately. The plasma concentrations of edoxaban and its metabolite, D21-2393, as well as the PD measures will be listed and summarized by age, dose and time point.

11.4.3. Safety Analysis

11.4.3.1. Analysis of Bleeding Events

The primary safety endpoint is the composite of major and CRNM bleeding events that occur during the Main Treatment Period: from the date of first dose of study drug to the Month 3 Visit, or to the date of last dose of study drug plus 3 days if study treatment is discontinued, whichever is earlier. This analysis will be based on CEC adjudication results.

The time to major or CRNM bleeding occurring during the Main Treatment Period will be compared between treatment groups for subjects in the Safety Analysis Set, using the Cox proportional hazards regression model with treatment group, concomitant usage of aspirin at baseline, and underlying disease (Kawasaki disease, Fontan surgery, heart failure or Other) as covariates. Hazard ratio between edoxaban and SOC treatment group will be calculated with corresponding 95% CI. The incidence, annualized event rate, and rate difference between edoxaban and SOC treatment groups will also be calculated.

In addition, incidence, annualized event rate and rate difference between edoxaban and SOC treatment groups with corresponding 95% CI will be calculated for following endpoints for Safety Analysis Set for the Main Treatment Period. Incidence and annualized event rate will also be calculated for the following endpoints occurring from the day after Month 3 Visit to date of last dose of study drug plus 30 days in the Extension Period.

- Major and CRNM bleeding event combined
- Major bleeding event
- All bleeding event (major, CRNM, and minor bleeding combined)

The above 3 categories of bleeding endpoints will also be summarized for the periods and subjects below:
- Incidence, annualized event rate, and rate difference will be calculated for events occurring from the date of first dose of study drug to the date of last dose of study drug plus 30 days for subjects who do not participate in the Extension Period.
- Incidence and annualized event rate will be calculated for events occurring from the day after Month 3 Visit to the data of last dose of study drug for subjects who participate in the Extension Period.

To assess the safety for intra-patient between the Main Treatment Period and previous anticoagulant regimen, bleeding history since diagnosis of underlying disease and within the past 3 months of randomization will be collected. The incidence of bleeding events and annualized event rate in the 3 months prior to randomization and during the Main Treatment Period will be calculated for the subjects who have both pre-randomization and post-randomization data available. This analysis will be based on Investigator reported events.

To compare edoxaban regimen with available existing historical control data for bleeding, a literature review and a search for registered clinical trials with similar endpoints will be conducted. The available results of control data will be extracted and tabulated together with the results of the Main Treatment Period from this study.

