5.2. Study Drug(s)

5.2.1. Description

The study drug for this study is edoxaban (DU-176b) and SOC anticoagulants (UFH/LMWH and VKA). The active ingredient is edoxaban tosylate and the international non-proprietary name is N-(5-Chloropyridin-2-yl)-N'-[(1S,2R,4S)-4-(N,N-dimethylcarbamoyl)-2-(5-methyl-4,5,6,7-tetrahydro[1,3]thiazolo[5,4-c]pyridine-2-carboxamido)cyclohexyl] oxamide mono (4-methylbenzenesulfonate) monohydrate.

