5.2.4.1. To Initiate Edoxaban Treatment at Randomization

For subjects without prior anticoagulant therapy, edoxaban may be started the day of randomization (Day 1).

For subjects who received VKA treatment prior to randomization and are randomized to edoxaban, VKA treatment will be discontinued the day before randomization and edoxaban dose will be initiated when an INR \leq 2.5 is reached. It is per Investigator's discretion based on his/her local practice and on the subject's underlying cardiac disease to consider if heparin bridging is necessary during this period. Heparin bridging will be provided by the Investigator.

If heparin bridging is used, edoxaban will be started as below:

- 1. In case of bridging with a LMWH twice a day regimen, edoxaban dosing will start 12 ± 3 hours after the last LMWH dose
- 2. In case of bridging with a LMWH once a day regimen, edoxaban dosing will start 24 ± 3 hours after the last LMWH
- 3. In case of bridging with a UFH regimen, edoxaban dosing will start 4 ± 1 hour after the last UFH dose

5.2.4.2 Transition SOC-Treated Subjects during the Main Treatment Period to Edoxaban in the Extension Period

For subjects who received VKA treatment edoxaban dosing will be initiated when an INR \leq 2.5 is reached. This may occur as early as next day of the Extension Period.

If the subject was originally randomized to UFH or LMWH, edoxaban will be started as below:

1. In case of LMWH twice a day regimen, edoxaban dosing will start 12 ± 3 hours after the last LMWH dose

- 2. In case of LMWH once a day regimen, edoxaban dosing will start 24 ± 3 hours after the last LMWH
- 3. In case of UFH regimen, edoxaban dosing will start 4 ± 1 hour after the last UFH dose

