5.2.4.3 To Initiate SOC Treatment

If the subject is randomized to the SOC treatment and they use locally sourced SOC, they will receive the following SOC anticoagulant treatment according to the clinical site's usual treatment practice (alone or in combination):

- LMWH (alone or with VKA)
- UFH (alone or with VKA)
- VKA (alone or with LMWH or UFH)

For subjects who do not receive VKA treatment prior to randomization and are randomized to SOC with VKA, VKA treatment may be started on the day of randomization (Day 1).

It is per Investigator's discretion based on his/her local practice and on the subject's underlying cardiac disease to consider if heparin bridging is necessary post-randomization until an INR between 2.0 and 3.0 is reached. Heparin bridging will be provided by the Investigator.

If centrally sourced SOC treatment is required from the Sponsor, the subject will be treated as follows:

- For subjects randomized to enoxaparin: Neonates or children receiving either once- or twice-daily therapeutic enoxaparin should be monitored as per local practice.
- For subjects randomized to warfarin, it is recommended that the dose should be titrated to achieve a target INR of 2.0 to 3.0. It is per Investigator's discretion based on his/her local practice and on the subject's underlying cardiac disease to consider if heparin bridging is necessary during this period. Visits will be at the discretion of the Investigator and captured as unscheduled visits for data collection. Adjustment of the maintenance dose of VKA will be dependent on INR monitoring as follows:
 - INR 2.0 to 3.0, no change in dose
 - INR 1.1 to 1.4, increase dose by 20%
 - INR 1.5 to 1.9, increase dose by 10%
 - INR 3.1 to 3.5, decrease dose by 10%

INR >3.5, hold VKA until INR is <3.5, then decrease dose by 20% when restarted.

To initiate SOC post screening, it is recommended to test infants and children every 4 weeks once a stable dose of VKA has been achieved. However, depending on the site's clinical practice and PI's discretion, the subjects can be tested at the physician's discretion and/or according to local practice. More frequent INR testing is recommended in infants and children receiving VKA with any change in diet or medication or when an illness occurs. An unscheduled visit will need

to be performed to document the discretionary INR measurement and potential VKA dosage change as an unscheduled visit day.

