6.4. Main Treatment Period

The Main Treatment Period is defined as the time from randomization until the end of Month 3 of treatment. All treatment comparative analyses will be made during this time period.

6.4.1. Subjects Randomized to the Edoxaban-Treatment Arm:

For subjects randomized to the edoxaban arm, a blood sample will be collected before the first dose of edoxaban for PD analysis only if the subject did not receive any heparin (UFH or LMWH) or VKA 24 hours prior to randomization.

6.4.2. Subjects Randomized to the SOC-Treatment Arm:

SOC will be provided by the Investigator. Alternatively, local supply depots within each country will provide SOC directly to the clinical sites. Subjects will be treated with heparin (UFH or LMWH) or VKA according to the site's SOC treatment procedure. However, if there are regulatory or clinical site hurdles providing the SOC, the Sponsor will provide SOC as enoxaparin or warfarin (see below).

If Investigators choose to use the SOC supplied by the Sponsor, the subject will be treated as follows:

- Enoxaparin Subjects will be treated with enoxaparin alone or as a bridging therapy in combination with warfarin during the initial study treatment period.
- For subjects in whom clinicians prescribe warfarin, this will be started on Day 1. Heparin bridging prior to reaching therapeutic levels by INR with warfarin may be performed depending on the clinical site's practice. Bridging therapy will be provided by the Investigator for the short duration. The subject will continue warfarin for the remainder of the study treatment period.

The Investigator will use discretion to decide when and how often to repeat INR or anti-FXa levels or aPTT measurements. These measurements will be taken in the clinic, or alternatively, optional clinical site-specific local laboratory (Appendix 17.1).

6.4.3. Monthly Visits (Months 1 and 2; Visits 3 and 4) for both arms:

Starting with Randomization, subjects will return to the clinic every 30 days ± 5 days (depending on the visit, see Schedule of Events in Appendix 17.1) until the Month 3 visit (Visit 5) or study withdrawal.

During study drug interruptions and after study drug discontinuation, subjects will be followed for the protocol-specified study procedures to assess the efficacy and safety endpoints and SAEs until the Month 3 visit (Visit 5). If a subject discontinues study drug prior to The Main Treatment

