11.4.1.1. Secondary Efficacy Analysis

The TE stated in this Section, include symptomatic thrombi in the systemic arterial or venous pathways (DVT, PE, stroke, SEE, intracardiac thrombus, and MI), and asymptomatic intracardiac thrombus identified by cardiac imaging.

The following secondary efficacy endpoints will be summarized by treatment group using incidence, and annualized event rate for both the Main Treatment Period and the Extension Period, as well the rate difference between edoxaban and the comparator with the corresponding 95% CI for the Main Treatment Period. The incidence of each component will also be summarized by treatment group. This analysis will be based on CEC adjudicated results.

- The combination of symptomatic TE in the systemic arterial or venous pathways including DVT, PE, stroke, SEE, intracardiac thrombus, MI, and asymptomatic intracardiac thrombus identified by cardiac imaging that occur from randomization to the Month 3 Visit.
- Deaths as a result of TE that occurs from randomization to the Month 3 Visit.
- All-cause mortality occurring from randomization to the Month 3 Visit.
- The combination of symptomatic TE in the systemic arterial or venous pathways including DVT, PE, stroke, SEE, intracardiac thrombus, and MI, and asymptomatic intracardiac thrombus identified by cardiac imaging, which occur from the day after the Month 3 Visit to the date of last dose of study drug plus 30 days for subjects who participate in the Extension Period.
- Deaths as a result of TE that occurs from the day after the Month 3 Visit to the date of last dose of study drug plus 30 days for subjects who participate in the Extension Period.
- All-cause mortality which occur from the day after the Month 3 Visit to the date of last dose of study drug plus 30 days for subjects who participate in the Extension Period.

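### The bleeding window opens at first dose, so some randomized time before edoxaban starts is not counted, while the same early days in the SOC arm generally are; the effect is probably small and cheap to check

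*Combined protocol and SAP*

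**What the plan says.** Section 11.4.3.1 counts major and CRNM bleeds "that occur during the Main Treatment Period: from the date of first dose of study drug to the Month 3 Visit", or to 3 days after the last dose if treatment stops sooner. Sections 2.1.1 and 2.3.1 use the same window.

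Section 6.4 gives the same period another start: "The Main Treatment Period is defined as the time from randomization until the end of Month 3 of treatment". It adds that all comparative analyses belong to that period. Section 3.2 agrees with 6.4. The efficacy endpoints also start at randomization, for example "All-cause mortality occurring from randomization to the Month 3 Visit" (Section 11.4.1.1).

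What counts as study drug, and when it starts, differs by arm:

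- Section 5.2.1 covers both arms: "The study drug for this study is edoxaban (DU-176b) and SOC anticoagulants (UFH/LMWH and VKA".
- Edoxaban arm, child on prior VKA (Section 5.2.4.1; also 5.1.1.1): "VKA treatment will be discontinued the day before randomization and edoxaban dose will be initiated when an INR" of 2.5 or lower is reached. The Investigator may "consider if heparin bridging is necessary during this period", and edoxaban then follows some hours after the last heparin dose.
- SOC arm (Section 5.2.4.3): a child not previously on a VKA may start it on Day 1. The Investigator is left "to consider if heparin bridging is necessary post-randomization until an INR between 2.0 and 3.0 is reached".

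Two passages limit the gap. Section 5.1.1 calls for dosing on the day of randomization when a prior-VKA child's INR is already 2.5 or lower. Section 6.3 allows the first dose on Day 1 or Day 2 and refers to Section 5.2.4.

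**The concern.** The start of the window depends on the assigned arm. A prior-VKA child assigned to edoxaban may spend randomized days on residual VKA or bridging heparin before the clock starts. A similar child assigned to SOC is already on what the plan calls study drug, so the clock starts at the first SOC dose. A bleed in those days is counted in one arm and not in the other.

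Benefit and risk also start at different times. A thromboembolic event in the gap is counted, provided the child later takes a dose and so enters the mITT set. A bleed in the same gap is not counted even then.

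Other planned outputs do not fill the hole:

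- The other bleeding summary in Section 11.4.3.1 that covers the first three months also starts at first dose.
- A bleed that begins and ends in the gap is not treatment-emergent under Section 11.4.3.3, so it would appear only in the by-subject listing.
- The intra-patient comparison is Investigator-reported and covers a subset. Whether it includes the gap depends on which definition of the Main Treatment Period applies.

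For efficacy, by contrast, Section 11.4.1.2 already has an analysis from randomization to the Month 3 Visit or last dose plus 3 days.

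**Working it through.** **1. The plan's own figure.** Section 11.6 gives 8.5% (edoxaban, n = 100) and 10.3% (SOC, n = 50), with a 95% CI for the difference of -11.8% to 8.2%.

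- Difference: 0.085 - 0.103 = -0.018.
- SE = sqrt(0.085 × 0.915/100 + 0.103 × 0.897/50) = sqrt(0.000778 + 0.001848) = 0.0512.
- -0.018 ± 1.96 × 0.0512 gives -11.84% to 8.24%.

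This reproduces the plan, and no figure in it is disputed.

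**2. Which randomized time is counted.**

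| Child | Between randomization and first dose | Counted for bleeding? |
|---|---|---|
| Edoxaban, no prior VKA | None or about a day | Yes, from first dose |
| Edoxaban, prior VKA, INR 2.5 or lower, not bridged | None or about a day | Yes, from first dose |
| Edoxaban, prior VKA, INR above 2.5 or bridged | Residual VKA, possibly heparin; no maximum wait stated | No, until edoxaban starts |
| SOC | No waiting rule written; VKA and heparin are study drug | Generally yes |

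Only the third row creates the difference between arms.

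**3. Expected bleeds left out.** The documents do not say how many children are in the third row, how long they wait, or how often they bleed meanwhile. The following are assumptions: 10 to 40 of the 100 edoxaban children, 1 to 7 days, and 1 to 3 times the SOC hazard, with the 10.3% risk spread evenly over 90 days.

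- SOC hazard: -ln(1 - 0.103)/90 = 0.001208 per day.
- Low: 10 × 1 × 0.001208 × 1 = 0.012 bleeds.
- High: 40 × 7 × 0.001208 × 3 = 1.01 bleeds.
- Expected edoxaban bleeds: 100 × 0.085 = 8.5. Shares: 0.012/8.5 = 0.1% and 1.01/8.5 = 11.9%.
- If every gap is one day, the high case is 40 × 1 × 0.001208 × 3 = 0.145, or 1.7%.

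A second set of assumptions uses 10 to 50 children, 1 to 5 days, and 1 to 5 times the edoxaban hazard of -ln(1 - 0.085)/90 = 0.000987 per day. It gives 0.01 to 1.23 bleeds; 30 children, 3 days and 3 times the hazard give 0.27.

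**4. Effect on the planning difference.** Adding 0.012 to 1.01 bleeds per 100 moves -1.80 points to between -1.79 and -0.79. In whole events:

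| Edoxaban bleeds added | Difference | 95% CI |
|---|---|---|
| 0 | -1.8% | -11.8% to 8.2% |
| 1 | -0.8% | -11.0% to 9.4% |
| 2 | +0.2% | -10.2% to 10.6% |

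**5. Rates and hazard ratio.** Starting at randomization adds person-time as well as events. The annualized edoxaban rate rises only if the gap hazard exceeds the hazard after first dose, about 0.00099 per day at planning rates. The multiples in step 3 lie above that, but nothing in the documents rules out a lower gap hazard, for instance with a falling INR and no bridge.

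**The case against.** The strongest reply is that the on-treatment window is deliberate. Section 2.1.1 writes it into the primary objective, and Sections 11.1 and 11.2 analyse safety by drug received. A bleed on residual VKA before any edoxaban is not edoxaban exposure. This stands as a reason to keep the first-dose analysis as primary. It does not explain why the same period has two start dates, or why no randomized comparison of bleeding accompanies the on-treatment one.

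The second reply is that the gap is short. Sections 5.1.1 and 6.3 do confine it mainly to prior-VKA children with INR above 2.5, or those bridged. Section 6.3 is permissive, however, and defers to Section 5.2.4, where the start depends on INR and no longest wait is given.

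The third is that the data exist: AEs are recorded from consent (Section 9.2) and suspected bleeds are adjudicated (Section 6). This is true, and it makes the remedy cheap.

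A reader might also infer more than the text supports:

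- *Every bleeding measure is biased in favour of edoxaban.* The direction is fixed for event counts only.
- *Bridging is treated oppositely in like patients.* The SOC text on Day 1 start and bridging mainly concerns children starting a VKA, whereas the edoxaban gap concerns children already on one. The fair contrast is between prior-VKA children in the two arms.
- *About 12% of edoxaban bleeds are lost.* That needs 40 children, 7 days and triple hazard together, and none of these is in the documents.

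**Conclusion.** The point holds as a matter of definition and completeness. The bleeding window has an arm-dependent start, and it conflicts with the Main Treatment Period in Sections 3.2 and 6.4. What counts as first dose is not stated by arm. Because Section 5.2.1 lists heparin as study drug, a bridging dose in the edoxaban arm could be read as a first dose, although the first edoxaban dose is the natural reading.

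The effect is probably small: about 0.01 to 1.0 of 8.5 expected edoxaban bleeds under the assumed ranges, against a CI half-width of about 10 points in a descriptive, unpowered study. It is still worth checking, because the planning difference is only -1.8 points and two uncounted bleeds would reverse its sign. The documents do not support calling the primary analysis invalid or the effect large. A cheap supplementary analysis is justified.

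**What to change.** Keep the first-dose, on-treatment analysis as primary, and make these changes:

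1. In Section 11.4.3.1, prespecify a supplementary analysis of adjudicated major plus CRNM bleeding with time zero at randomization, in the Randomized Analysis Set by assigned arm. End it at the Month 3 Visit or last dose plus 3 days, whichever is earlier; for never-dosed subjects, end it at the Month 3 Visit. Report incidence, the rate difference with 95% CI, and the same Cox model. The Safety Analysis Set would not do here: it drops a child who bleeds in the gap and never starts treatment, so it conditions on a later dose.
2. List bleeds between randomization and first dose by arm, including never-dosed subjects.
3. State what counts as first dose of study drug in each arm.
4. Give the on-treatment bleeding window its own name in Sections 2.1.1, 2.3.1 and 11.4.3.1, so that it no longer conflicts with the Main Treatment Period in Sections 3.2 and 6.4.

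No change to washout or bridging rules is implied. The cost is wording, one more table and a listing, using data already collected. The edoxaban figure may come out slightly less favourable.

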5. STUDY TREATMENT(S)

5.1. Assigning Subjects to Treatments and Blinding

5.1.1. Treatment Groups

All subjects will be assessed for eligibility in the study in accordance with the inclusion/exclusion criteria. Eligible subjects will be stratified and randomized as follows:

• All eligible subjects will be stratified by:

Type of underlying heart disease:

Kawasaki disease

Fontan surgery

Heart failure (HF)

Others (which can include post-surgical procedures for congenital heart disease other than Fontan surgery)

Subjects with underlying disease other than Kawasaki will be further stratified by concomitant use of low dose aspirin (1 to 5 mg/kg/day).

• Randomized in a 2:1 ratio (edoxaban:SOC, respectively) into 1 of 2 treatment arms:

Edoxaban-treatment arm: subjects will receive a selected dose of edoxaban

OR

SOC-treatment arm: subjects will receive SOC anticoagulant according to clinical site's SOC treatment, as follows (alone or in combination):

Heparin, including UFH or LMWH

Vitamin K antagonist (VKA) with potential bridging with heparin based therapy until VKA INR is in therapeutic range

After Month 3, all subjects who continue in the Extension Period and are on SOC will be offered edoxaban treatment and dosed according to their cohort age at the time of subject consent. During the extension period of the study, check the body weight prior to dosing and adjust dosage accordingly. Frequency of dosage changing is up to the Investigator's discretion.

Subjects from 1 to <18 years of age will be enrolled in the study as soon as the dosing regimen is established for each age cohort in the Phase 1 single-dose U157 study.

Additionally, subjects less than 1 year of age will be admitted to the study after review by the IDMC of safety data of 50% of subjects in the 1 to <18 years of age group who have completed the Main Treatment Period of 3 months (50 subjects in edoxaban arm and 25 subjects in SOC arm).

Subjects younger than 6 years of age will only receive edoxaban granules for oral suspension, which will give more flexibility to adjust mg/kg dose. Doses for all age groups will be selected to elicit target exposures comparable to those achieved from the adult Phase 3 study of 60 mg.

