11. STATISTICAL METHODS

11.1. General Statistical Considerations

All efficacy analyses will be based on the modified intention-to-treat (mITT) Analysis Set and will be performed based on the treatment group assigned at randomization.

Safety analysis will be performed using the Safety Analysis Set. Subjects will be analyzed according to actual treatment received.

All analyses for the Extension Period will be based on subjects who participate in the Extension Period and take only edoxaban in the Extension Period, in the specified analysis set, and will be summarized for the edoxaban treatment group. Data listings will be prepared for subjects who are randomized to the SOC arm, participate in the Extension Period, and do not switch to edoxaban right after the Month 3 Visit.

All confidence intervals will be descriptive and will be two-sided 95% confidence interval (CI), unless otherwise specified.

Unless otherwise specified, the baseline value of an efficacy variable for a subject is the last nonmissing measurement before the randomization, and the baseline value of a safety variable is the last non-missing measurement before the first dose of the study drug.

In general, missing data will not be imputed for the purpose of data analysis. No visit windows will be used for analysis.

Continuous variables will be summarized by the number of observations, mean, standard deviation, median, and minimum and maximum values. Categorical variables will be summarized using frequency counts and percentages. Summary statistics will be presented by treatment group.

There is no formal statistical interim analysis planned. However, after the first 50 subjects enrolled in the edoxaban treatment group and 25 subjects enrolled in the SOC treatment group complete the first 3-month treatment period, an interim assessments by IDMC of safety endpoints will be performed to allow for enrollment of subjects <1 year of age into study.

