11.6. Sample Size Determination

A sample size of 150 subjects was chosen for this study. This study is not a powered study intended to draw conclusions based on statistically significant differences between edoxaban and SOC. An adequately powered study would be unachievable due to the significantly large sample size required and the enormous challenge to enroll these pediatric patients. Although the sample size is not based on statistical consideration, assuming major and CRNM bleeding event rates (which are the primary endpoints for this study) are the same as observed in adult Hokusai-VTE Study, (ie, 8.5% and 10.3% in edoxaban and SOC arms, respectively); with 100 subjects in edoxaban arm and 50 subjects in standard of care arm, the 95% CI around the point estimate of the risk difference between edoxaban and SOC is -11.8%, 8.2%..

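### The primary bleeding hazard ratio comes from a five-coefficient Cox model on about 14 expected events with no small-sample method named; Firth's penalised fit is modestly better and gives a finite estimate even when one arm has no events

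*Combined protocol and SAP*

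**What the plan says.** Section 11.4.3.1 compares the arms on time to major or clinically relevant non-major bleeding in the Safety Analysis Set, "using the Cox proportional hazards regression model with treatment group, concomitant usage of aspirin at baseline, and underlying disease", with disease in four categories (Kawasaki, Fontan, heart failure, other). The hazard ratio is reported with a 95% confidence interval. The synopsis describes the same model. The section adds: "The incidence, annualized event rate, and rate difference between edoxaban and SOC treatment groups will also be calculated".

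Allocation is 2:1 (Section 5.1.1), within strata of underlying disease; "Subjects with underlying disease other than Kawasaki will be further stratified by concomitant use of low dose aspirin". That makes seven strata: Kawasaki, and three other disease groups each by aspirin.

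Section 11.6 takes its rates from an adult venous thromboembolism study, "8.5% and 10.3% in edoxaban and SOC arms, respectively", "with 100 subjects in edoxaban arm and 50 subjects in standard of care arm". It describes the trial as unpowered. Section 11.1 states: "All confidence intervals will be descriptive and will be two-sided 95% confidence interval (CI), unless otherwise specified".

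Neither Section 11.4.3.1 nor the synopsis names an estimation method for the Cox model, or says what happens if an arm or covariate level has no events. Section 11.7 leaves further methods to a statistical analysis plan to be finalised before database lock; no separate text of that plan is in the document supplied.

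**The concern.** The model spends one coefficient on treatment, one on aspirin and three on disease, with fewer than three expected events for each. An unqualified Cox model is normally fitted by ordinary partial likelihood, which does badly with so few events in two ways:

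- If an arm has no events, the treatment hazard ratio has no finite estimate or usable Wald interval.
- Short of that, the log hazard ratio is more variable than it needs to be.

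The trial has no power target or margin, so its product is its estimates and intervals. The hazard ratio is the only model-based comparison specified for the primary endpoint, and it is most likely to be lost when bleeding is rare.

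**Working it through.** **Inputs.** From Section 11.6: risks 8.5% (edoxaban) and 10.3% (standard of care), with 100 and 50 subjects. From Section 11.4.3.1: the model terms.

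**The plan's own figure.** Section 11.6 says "the 95% CI around the point estimate of the risk difference between edoxaban and SOC is -11.8%, 8.2" per cent. An unpooled Wald interval reproduces it: d = 0.085 - 0.103 = -0.018; SE = √(0.085×0.915/100 + 0.103×0.897/50) = 0.05124; d ± 1.96×SE = -11.84% to 8.24%. The inputs are therefore read as the plan intends.

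**Events per coefficient.** Events: 8.5 + 5.15 = 13.65. Coefficients: 1 + 1 + 3 = 5. Ratio: 13.65/5 = 2.7.

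**Precision of the hazard ratio.** Planning value: ln(1-0.085)/ln(1-0.103) = 0.82 (log -0.20). Unadjusted SE of the log: √(1/8.5 + 1/5.15) = 0.558, so the 95% interval is about 0.27 to 2.44.

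**Probability that no finite hazard ratio exists.** With a = (1-p)^50 for standard of care and b = (1-p)^100 for edoxaban, the chance that at least one arm is empty is a + b - ab. Rates below 100% of plan are assumptions.

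| Rates relative to plan | Expected events | No SOC event (a) | No edoxaban event (b) | No finite hazard ratio |
|---|---|---|---|---|
| 100% | 13.65 | 0.44% | 0.01% | 0.45% |
| 75% | 10.24 | 1.8% | 0.1% | 1.9% |
| 50% | 6.83 | 7.1% | 1.3% | 8.3% |
| 25% | 3.41 | 27.1% | 11.7% | 35.6% |

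**Ordinary against Firth fit.** Simulation used 150 subjects, 2:1 blocks within the seven strata, no dropout, and 1,500 trials per row. The documents give no disease or aspirin mix, so the mixes are assumed: A is 25% in each disease group; B is Kawasaki 10%, Fontan 45%, heart failure 20%, other 25%. Aspirin shares, in the same order, are 80%, 50%, 20% and 40%. Bias, error and coverage of Wald intervals are for the treatment log hazard ratio, in trials where the ordinary fit is finite. Paired entries are ordinary / Firth.

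| Scenario | Some covariate level has no events | Ordinary fit not finite | Bias | RMSE | Coverage |
|---|---|---|---|---|---|
| A, planning rates | 11% | 0.3% | +0.04 / -0.01 | 0.637 / 0.571 | 96.5% / 97.4% |
| B, planning rates | 32% | 0.5% | +0.03 / -0.02 | 0.621 / 0.557 | 97.2% / 98.1% |
| B, unequal disease and aspirin risks | 69% | 1.0% | +0.05 / 0.00 | 0.645 / 0.575 | 97.8% / 98.4% |
| B, half rates | 71% | 7.1% | -0.08 / -0.15 | 0.794 / 0.674 | 98.0% / 98.9% |

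In A the reduction in RMSE is 1 - 0.571/0.637 = 10%, and in B it is 1 - 0.557/0.621 = 10%. Further simulation put it at roughly 5-10% at planning rates, with profile-likelihood coverage of about 95-96% for Firth and ordinary-fit failure of about 0.5% at planning rates and about 9% at half rates. The exact half-rate value, 8.3%, lies between the two simulated ones.

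**Weighting the rate difference over the seven strata.** At planning rates, under three risk patterns, the sampling SD of the crude and Mantel-Haenszel differences was 0.0517/0.0517, 0.0509/0.0509 and 0.0495/0.0495. Coverage was 93.8-94.5% for crude and 93.7-93.9% for Mantel-Haenszel with the Sato standard error.

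**The case against.** **The stakes are low.** All intervals are descriptive, no decision rule uses the hazard ratio, and incidence and the rate difference are reported beside it, so a comparison survives even if the hazard ratio does not. This stands, and it limits the weight of the point.

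**The plan is silent rather than wrong.** It does not say ordinary partial likelihood; it names no method and defers detail to a later plan. This also stands. If that plan already names a small-sample method, the point is met.

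**Firth has a cost.** The planning log hazard ratio is already negative, so a negative bias moves it further from the null, in edoxaban's favour. That direction matters for the hypothesis in Section 2.2 that edoxaban is at least as safe. The bias is small against an RMSE near 0.57 at planning rates. At half rates it is larger (-0.15 against -0.08), although those figures exclude the trials where the ordinary fit failed. This is a reason to show the ordinary fit alongside, not to avoid Firth.

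**Two stronger readings are not supported.**

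- A reader might infer that the hazard ratio will often be unusable, because a disease or aspirin level has no events in many simulated trials. Such a level makes its own nuisance coefficient diverge; the treatment hazard ratio stayed finite unless an arm was empty. Failure in about 20% of trials needs rates near 3.0% and 3.6%, which the documents do not give.
- A reader might infer that the rate difference should be weighted over the seven strata because the crude interval is too wide. The sampling spread is identical and coverage is no better, so a slightly narrower weighted interval is not a precision gain. Section 11.4.3.1 also lists the rate difference next to an annualized rate, whereas Section 11.6 speaks of a risk difference, so a binomial weighting might not target the planned quantity.

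**Conclusion.** The point holds in a limited form. Five coefficients on 13.65 expected events, with no small-sample method named, is a weak specification for the primary hazard ratio, and a better one is available at little cost. At the planning rates the gain is a roughly 5-10% lower RMSE and removal of a failure risk of about 0.5%. If true rates were half the adult ones, the failure risk would be about 8-9%.

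The failure probabilities rest on the plan's sample sizes and rates, or stated fractions of them. The RMSE, bias and coverage figures also depend on the assumed disease and aspirin mix. Firth does not narrow the interval materially: its mean standard error at planning rates was about 0.60 against 0.61. The case for it is stability, not power. The documents give no ground for changing the rate difference to a stratum-weighted form.

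**What to change.** In Section 11.4.3.1, the synopsis and the analysis plan, before database lock:

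- Fit the same five-coefficient Cox model by Firth's penalised partial likelihood, and report the hazard ratio with a profile-likelihood 95% confidence interval.
- Keep the ordinary Cox fit as supportive, and report it as not estimable when an arm has no events.
- State that no hazard ratio is given if the whole trial has no events. At half rates that chance is 0.0711 × 0.0130 = 0.09%.

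Leave the rate difference unweighted.

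The cost is wording and a small amount of programming: the penalty is a model option in SAS PHREG, and Section 11.7 already names SAS. No new data, subjects or visits are needed. The statistical price is the finite-sample bias, about -0.01 to -0.04 in most planning-rate runs, which the analysis plan should acknowledge.
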